Also, initial baseline vital signs (heart rate, blood pressure, respiratory rate, and oxygen saturation) will be obtained. EtCO₂ will be obtained at baseline and periodically using an oral/nasal sample line with the CapnostreamTM 20p monitor (Medtronic, Minneapolis, MN). The study will use a double limb circuit ICU ventilator Puritan BennettTM (Medtronic, Dublin, Ireland).

We will evaluate 4 NIPPV masks (2 oronasal masks and 2 full face masks).

[figure not shown]
Oronasal masks will be labeled as group A and numbered as A1 and A2; while full face masks will be labeled group B and numbered as B1 and B2. Order of the masks will be randomly chosen in two steps. First steps will be choosing A or B then randomly assign mask in each of these groups. We will randomly assign mask in group A or B by drawing an initial mask from the group and then continue the sequence of masks from that point.

For example, we randomly chose group A, then randomly chose A2, the sequence will be A2, A1. Then we would randomly choose B2, then the sequence would be B2, B1.

All subjects will perform 15 minutes on each mask followed by 5 minutes wash out interval between masks. EPAP levels will be 0, 2, 4, & 5 while IPAP remains at 5 higher than EPAP. EtCO₂ will be collected at 4:00, 4:30 and 5:00 minute mark. These three measures should differ by less than 20% of their average. Also, subjective mask

comfort will be assessed via visual analog scale (VAS) with 1 referring to least comfortable and 5 being the most comfortable after 5 each EPAP setting.

Procedure figure:

4- Subject Population:

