4.4.2. Facial surgery or deformity

4.4.3. Ear infection

4.4.4. History of pulmonary or cardiac disease

5- Research recruitment and Consent Procedures:

5.1. Subjects will be recruited from students enrolled, faculty, and staff at Rush University.

5.2. An informed consent will be obtained by the investigators for all eligible candidate that meet the criteria.

6- Compensation:

Volunteers will be compensated with \$ 25 Visa gift card

7- Special precautions:

- 7.1. Subjects refrain from eating at least 60 min before the study
- 7.2. Study will be stopped if HR change by 20% from baseline for more than 1 min.
- 7.3. Study will be stopped if subjects complain of shortness of breath

8- Confidentiality:

Subject names, date of birth, and contact information (email) will be stored in REDCap. However, only de-identified data will be used for analysis.

9- Data Collection Instruments/ Data Collection Procedures/Data Analysis Plan:

Data for each subject will be recorded in REDCap

10- Variables:

Dependent: CO₂ clearance, level of comfort-

Independent: NIPPV interface, level of EPAP

11- Limitation:

It is performed on healthy subjects.

12- Analysis:

Data will be recorded in REDCap. Demographics data age (interval), gender (nominal),

ethnicity (nominal) will be collected. HR (continuous), RR (continuous), SpO2

(continuous), ETCO₂ (continuous), EPAP (ordinal), IPAP (ordinal) will be collected.

Means and Standard deviations will be calculated for aforementioned data. NIPPV interfaces number, sizes will be collected. Level of comfort will be collected; median and interquartile ranges will be calculated. Relationship between dependent variable ETCO₂ and independent variable EPAP level will be analyzed by a Kruskal-Wallis test to determine if a significant difference exists. If a significant difference is found a Mann-Whitney U Test will be used to determine which EPAP levels significantly differ. Relationship between dependent variable comfort level and independent variable NIPPV interfaces will be analyzed a Kruskal-Wallis test to determine if a significant difference exists. If a significant difference is found a Mann-Whitney U Test will be used to determine which masks were significantly more comfortable.

Literature cited:

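### Section 12 follows each Kruskal-Wallis test with six unadjusted, unpaired comparisons on the same 20 volunteers; paired tests with a Holm adjustment would repair both faults

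*Combined protocol and SAP*

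**What the plan says.** Section 3 (Methods) describes a randomized crossover in which every volunteer uses all four masks, and it sets the pressures: "EPAP levels will be 0, 2, 4, & 5". Section 4.2 gives 20 subjects. EtCO₂ is read three times per setting, and comfort is scored from 1 to 5 for each EPAP setting.

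Section 12 (Analysis) says that EtCO₂ by EPAP level "will be analyzed by a Kruskal-Wallis test to determine if a significant difference exists". The follow-up is: "If a significant difference is found a Mann-Whitney U Test will be used to determine which EPAP levels significantly differ". Comfort by mask has the same two steps: "If a significant difference is found a Mann-Whitney U Test will be used to determine which masks were significantly more comfortable".

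Neither Section 12 nor any other section states an alpha, names an adjustment for the pairwise tests, mentions pairing, or says how repeated readings are combined.

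**The concern.** The pairwise step produces the study's conclusions: it names the EPAP levels that differ in CO₂ washout, and it says "which masks were significantly more comfortable". Its only protection is the preceding omnibus test. That gate controls the family error when all four levels are equal. It does not do so when some differ and others are equal: a real difference opens the gate, and the equal pairs are then each tested at the full level. A study that looks for the pressure at which washout becomes adequate should expect that mixed pattern.

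The second fault bears on the first. Kruskal-Wallis and Mann-Whitney tests assume independent groups, but the same volunteers supply every level. Any error rate quoted for this plan therefore has to say which form of test it describes.

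**Working it through.** **Inputs.** Four EPAP levels and four masks (Section 3); 20 volunteers (Section 4.2); omnibus test, then pairwise tests (Section 12). Assumed, because the documents give no figure: two-sided alpha of 0.05 per test, the within-subject correlation, and the size of any true difference. The plan states no family-wise rate, so there is no figure of its own to reproduce.

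**Family size.** 4 × 3 / 2 = 6 pairs for EPAP and 6 for masks.

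**Independent values.** With k equal levels left after the gate opens, the chance of at least one false pair is approximately P(range of k standard normals > 1.96 × √2).

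- No level differs: the gate limits the rate to about 5% (4.9% simulated, n = 20 per level). Without the gate, k = 4 would give 20.3%.
- One level differs clearly and three are equal: k = 3 gives 12.2% (about 12-13% simulated with a 3 SD shift; 11.5% with ordinal scores).
- Two equal pairs: 1 − 0.95² = 9.75% (9.6% simulated).
- All four differ: there is no true-null pair, so the rate is zero.

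**Size of the true difference** (one level shifted, independent groups, n = 20):

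| Shift | Gate opens | Family error |
|---|---|---|
| 0.5 SD | 28% | 6.9% |
| 0.75 SD | 62% | 11.2% |
| 1 SD | 88% | 12.0% |
| 1.5 SD | 99.7% | 12.2% |

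**Planned unpaired tests on crossover data** (one value per volunteer per level, one level shifted 3 SD). With within-subject correlation ρ, the variance of a difference between two levels falls by the factor 1 − ρ. The Mann-Whitney test takes no account of this, so it rejects too seldom. Separate simulation runs gave these ranges:

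| Assumed ρ | Family error |
|---|---|
| 0.3 | 4.7-5.8% |
| 0.5 | 1.5-2.6% |
| 0.7 | 0.2-0.6% |

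Pooling the four masks (80 values per level) gave nearly the same: 5.9%, 2.4% and 0.4%.

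**Three readings entered as separate values.** Pooled over masks this is 20 × 4 × 3 = 240 values per level. If the readings share an assumed 90% of the within-subject variance, the one-level-differs case gives 48%, 37%, 23% and 11% at ρ = 0, 0.3, 0.5 and 0.7.

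**Correctly paired tests.** Friedman, then unadjusted Wilcoxon signed-rank tests, gave about 11-13.5% in the one-level-differs case across the correlations tried. The inflation thus returns once the pairing is respected.

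**With Holm.** When one level clearly differs, its three pairs are rejected first. The three null pairs are then tested starting at 0.05 / 3 = 0.0167, for which the range formula gives 4.4%. Simulated family error with paired tests was about 3.5-4.5%.

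**The case against.** The strongest objection is that 12% does not describe the tests the plan names on the data it will collect. The same volunteers appear at every level, zero correlation is implausible, and at moderate correlation the planned unpaired tests give about 5% or less. A Holm adjustment added to the Mann-Whitney tests would only make a conservative procedure more so. This stands, and it is why the adjustment should not be recommended without the change of test. It does not clear the plan, because the low rate is a by-product of the wrong test. It depends on a correlation that nobody has stated, it costs power, and it can reverse if the three readings are entered separately.

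Two further points stand. The gate does not open almost every time once any difference exists; with a 0.5 SD shift it opened in 28% of runs. And this is a 20-volunteer student project that makes no confirmatory claim, so a modest error rate in exploratory comparisons would be tolerable if it were declared.

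A reader might infer that the trial carries a 12% false-positive rate in place of a promised 5%. The documents do not support that. They promise no rate, and 12% is approximately a ceiling for one pattern of true effects, under independence or correct pairing. A reader might also combine the families as 1 − (1 − 0.122)² = 23%. That needs the worst pattern in both families, independence between EtCO₂ and comfort, and a shared error budget, none of which the plan sets out.

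**Conclusion.** The point holds in conditional form. Section 12 leaves six pairwise tests per family unadjusted, and the Kruskal-Wallis gate does not protect equal pairs once another level differs.

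At an assumed two-sided 0.05, the family error for independent values or correctly paired tests is up to about 12%, 9-10% or 5%, according to whether three levels, two pairs or all four levels are equal. For the unpaired tests as written, even the direction of the error is unknown. It is below these figures with one value per volunteer per level, and possibly well above them if readings are treated as independent.

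The structural facts (six pairs, no adjustment, pairing ignored) come directly from the text. The percentages rest on assumed alpha, correlation and effect size. The plan should be changed, and the pairing is the larger of the two faults.

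**What to change.** Amend Section 12 as follows:

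- State alpha and sidedness.
- Average the three EtCO₂ readings to one value per volunteer per condition. If EPAP levels are compared over all masks, average over masks as well. State likewise how the comfort scores from the different EPAP settings become one value per volunteer per mask.
- Replace Kruskal-Wallis with Friedman, and Mann-Whitney with Wilcoxon signed-rank.
- Holm-adjust the six pairwise p-values within each family (EtCO₂ by EPAP; comfort by mask) and report the adjusted values. If EPAP levels are compared separately for each mask, apply Holm within each mask's set of six.

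The cost is a few sentences and no extra data. Each pair has slightly less power than under unadjusted paired tests, since at alpha 0.05 the smallest of six p-values must be below 0.05 / 6 = 0.0083. That is attainable with 20 volunteers: even eight non-zero differences, all in one direction, give an exact two-sided p of 2 / 2⁸ = 0.0078. Relative to the plan as written, the paired tests recover power that the unpaired ones lose when a volunteer's values are positively correlated.

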Student Research Project Proposal

Title:

Carbon Dioxide (CO₂) Clearance from various face masks in Normal Volunteers at various level of Expiratory Positive Airway Pressure (EPAP) when Using a Non-Invasive Positive Pressure Ventilation (NIPPV)

Investigators:

Mentor:

[name], MHS, RRT, FAARC, FCCP

Graduate Student:

[name], Respiratory Care Department, Rush University.

Study aim:

Determine the EPAP (baseline pressure) required to effectively wash out CO₂ for current available masks, and assess perceived level of comfort with each mask with using noninvasive ventilator.

1- Abstract:

Background: Noninvasive positive pressure ventilation (NIPPV) can be delivered via single limb circuit or double limb circuit ventilators. There are many advantages to NPPV. However, a reasonable number of questions remain unanswered, such as mask impact on carbon dioxide (CO₂) clearance based on EPAP level.

Objective: Determine the EPAP (baseline pressure) required to effectively wash out CO₂ for each mask, and assess perceived level of comfort with each mask with ICU ventilator.

Method: This study will be a randomized crossover trial that will be conducted at Rush University. The study will be conducted with 20 healthy volunteers who will be placed on ICU ventilator operating in the NIPPV mode. All subjects will perform 15 minutes of breathing on NIPPV on each mask of the 4 different masks (2 oronasal and 2 full face masks) that are randomly selected. Breathing through each mask will be followed by a 5-minute wash out period between masks. End tidal Carbon Dioxide (EtCO₂) will be sampled nasal/oral. Different levels of EPAP will be set and CO₂ clearance will be monitored. Additionally, subjective mask comfort will be assessed via visual analog scale (VAS) with 1 referring to least comfortable and 5 being the most comfortable.

2- Introduction

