via EtCO₂. Masks B & C both had higher rate of total leaks due to higher rate of unintentional leaks which may improved CO₂ wash out, hence, led to no differences in PtcCO₂.⁸ Another study compared total face mask against oronasal mask impact on gas exchange (PvCO₂) favors total face mask in the first 6 hours and during the acute phase of respiratory failure using NIPPV.⁷ Both Medrinal and Sadeghi assessed gas exchange not masks' CO₂ clearance. Since the intentional leak impacts CO₂ clearance, and the intentional leak level depends on the level of pressure.⁸ The previous studies didn't study different level of EPAP (baseline pressure). One level of EPAP pressure of 4 cm H₂O was used in Medrinal study based on Samolski's finding.⁸ While in Sadeghi's study, IPAP started at 10 cm H₂O and EPAP started at 4 cm H₂O. IPAP and EPAP were increased gradually based on subjects' need, therefore it lacked consistency in EPAP level.⁹

ICU ventilators using double limb circuit is an alternative to deliver NIPPV, however, researches on minimum baseline pressure required to prevent CO₂ rebreathing is not clear as well. In a study that compared 3 types of masks (2 ONM and 1 FFM) to helmet in acute hypercapnia respiratory failure. NIPPV in both group improved arterial blood gases. ICU ventilators settings in masks group used positive end expiratory pressure (PEEP) referring to baseline pressure that ranged from 3 – 5 cm H₂O (mean 4.26 ± 1.92); and inspiratory pressure adjusted to achieve tidal volume of 6-8 ml/kg (16.37 ± 4.19). On the other hand, settings for helmet groups were ~ 30%.¹¹

The answer regarding effective EPAP level to wash out CO₂ remains uncertain. The purpose of this study is to compare the efficacy of CO₂ clearance between different NIPPV interfaces (oronasal and full face masks) when using double limb circuit ICU

ventilator at lower levels of EPAP. The aim of this study is to determine the EPAP (baseline pressure) required to effectively wash out CO₂ for each mask and assess perceived level of comfort with each mask.

3- Methods:

This study will be a randomized crossover trial that will be conducted at Rush University.

Normal volunteers will be recruited from Rush University Medical Centers. Volunteers will be screened with inclusion and exclusion criteria and an informed consent is required in order for them to participate. Demographic (age, gender, ethnicity) will be obtained.

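### The planned EtCO₂ tests compare EPAP levels only with one another, so they cannot say which EPAP is sufficient for any mask

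*Combined protocol and SAP*

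**What the plan says.** The Objective in the Abstract (section 1) is to "Determine the EPAP (baseline pressure) required to effectively wash out CO₂ for each mask", and the end of the Introduction (section 2) repeats it: "determine the EPAP (baseline pressure) required to effectively wash out CO₂ for each mask and assess perceived level of comfort with each mask". Section 10 names CO₂ clearance as a dependent variable, and mask and EPAP level as the independent ones.

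Section 3 (Methods) supplies the data:
- Source of the EtCO₂ values: "EtCO₂ will be obtained at baseline and periodically using an oral/nasal sample line"
- Ventilator settings compared: "EPAP levels will be 0, 2, 4, & 5 while IPAP remains at 5 higher than EPAP"
- Timing of the readings: "EtCO₂ will be collected at 4:00, 4:30 and 5:00 minute mark"
- Time allotted per mask: "All subjects will perform 15 minutes on each mask followed by 5 minutes wash out interval between masks"

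The three timed readings must agree within 20% of their average.

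Section 12 calculates means and SDs for the collected variables, EtCO₂ among them. It tests EtCO₂ across EPAP levels by Kruskal-Wallis and, if that is significant, "a Mann-Whitney U Test will be used to determine which EPAP levels significantly differ". Mask is a tested factor only for comfort.

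**The concern.** The aim is a sufficiency question asked mask by mask: at which EPAP is CO₂ cleared well enough? Answering it needs a reference or threshold for EtCO₂ and an analysis within each mask. Section 12 states neither. A significant result says that some levels differ, not that the better one is good enough. A non-significant result is compatible with all levels clearing CO₂ and with none doing so. If the criterion is chosen after the data are seen, the answer to the main question becomes post hoc.

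**Working it through.** **1. Is there a criterion or reference anywhere in the document?** Four candidates were checked.
- The 20% rule (section 3) concerns agreement of three repeat readings. It is a stability check.
- EPAP 0 is not an untreated control, because IPAP is still set 5 above it.
- The 4 cm H₂O in the Introduction is another study's finding with a single-limb circuit. This trial uses a double-limb ICU ventilator.
- Baseline EtCO₂ is collected and may enter the means and SDs, but no test or interval uses it.

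**2. What the rank tests can see.** For one mask with 20 subjects and 4 levels, N = 80 and H = 12/[N(N+1)] × Σ(Rⱼ²/20) − 3(N+1), where Rⱼ is the rank sum of level j. Adding a constant to all 80 values leaves every rank, and therefore H, p and each Mann-Whitney U, unchanged. This is algebra and needs no assumed SD. In a simulated example, adding 6 mmHg at all four levels left H = 0.057 and p = 0.996, while the mean change from baseline moved from about −0.2 to about +5.8 mmHg. If the masks are pooled, a rise common to all of them is just as invisible.

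**3. Rejection rates for contrasting truths.** One mask, n = 20, 4,000 simulated trials, two-sided 5% tests. Between-subject SD 3 and within-subject SD 1.5 mmHg are assumed.

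| True rise over baseline by level (mmHg) | Levels back at baseline | Kruskal-Wallis rejects |
|---|---|---|
| 0 / 0 / 0 / 0 | all | about 0% |
| 4 / 4 / 4 / 4 | none | about 0% |
| 4 / 2 / 0 / 0 | two | about 99% |
| 8 / 6 / 4 / 4 | none | about 99% |

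Within each pair of rows the test behaves the same although the right answers differ. A paired test against baseline separates the first two rows (about 5% against 100% rejection per level).

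**4. What 20 subjects could give instead.** Section 4.2 gives 20 without inputs, so there is no calculation to reproduce. Assume a total SD of 5 mmHg and a correlation ρ shared by baseline and on-mask values. SD of change = 5√[2(1−ρ)]. The one-sided 95% bound lies t(0.95, 19) × SD/√20 above the mean change. The two-sided 95% half-width for a paired contrast of two levels within a mask is t(0.975, 19) × SD/√20.

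| ρ | SD of change | One-sided bound | Paired half-width |
|---|---|---|---|
| 0.5 | 5.00 | 1.93 | 2.34 |
| 0.7 | 3.87 | 1.50 | 1.81 |
| 0.8 | 3.16 | 1.22 | 1.48 |
| 0.9 | 2.24 | 0.86 | 1.05 |

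**5. Does the schedule supply the cells?** A per-mask answer needs 4 masks × 4 levels = 16 cells per subject. If each level is held to its 5:00 reading, a mask takes 4 × 5 = 20 minutes, against the 15 stated. Fifteen minutes holds three levels, which is 12 of the 16 cells. The comfort rating, "5 being the most comfortable after 5 each EPAP setting", is also attached to each setting.

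**The case against.** The strongest case for the plan has five parts.

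- **A second purpose.** The Introduction also sets out to compare CO₂ clearance between interfaces, and contrasts between conditions suit a comparison. This stands as a reading of the Introduction. It does not rescue section 12, whose EtCO₂ tests do not name mask.
- **A descriptive route.** Baseline EtCO₂ and EtCO₂ means are already planned, so a formal test against baseline is one remedy among several. This stands: a stated descriptive criterion would also close the gap. As written, though, the summaries are not by mask and level, are not changes from baseline, and lead to no rule.
- **Baseline is an imperfect reference.** It is taken without support, so change from baseline mixes the effect of support with rebreathing. Contrasts between EPAP levels hold the set IPAP−EPAP difference constant. This stands in full, and is why both should be reported.
- **The illustration rests on one SD.** This stands. At a 2 mmHg margin and true change 0, the chance that the highest level fails is 47–1% with SD 5, but 11–0% with SD 3 and 71–22% with SD 8.
- **The timing conflict is a separate matter.** The procedure figure is not shown and may resolve it. It matters here only because the per-mask answer needs every cell.

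**Conclusion.** The concern holds. Carried out exactly as written, section 12 cannot identify a sufficient EPAP for any mask, whether its tests are significant or not. That conclusion follows from the invariance of ranks and the absence of a criterion, and depends on no assumed value. The precision figures do depend on assumptions, because the document gives no SD, correlation or margin. The change should be made before enrolment. It is mostly a matter of wording, and the kinds of measurement needed are already planned.

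**What to change.** **In section 12:**
- Analyse EtCO₂ by mask and EPAP level as the within-subject change from the subject's own baseline, with a confidence interval.
- Before enrolment, define effective washout. One option is that the one-sided 95% upper bound of the mean change lies below a margin chosen by the investigators, reporting for each mask the lowest EPAP from which all higher tested levels also pass. A stated descriptive criterion on the mean change and its interval would also do.
- Report within-mask, within-subject contrasts between EPAP levels alongside.
- State as a limitation that a pass means no EtCO₂ rise beyond the margin, not absence of rebreathing.

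**In section 3:** confirm that the baseline reading precedes the first mask, if the figure does not already show it. Reconcile the 15 minutes per mask with four levels read to 5:00.

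**Cost.** No new type of measurement is needed. Whether the schedule yields every cell cannot be said until the times are reconciled. The margin option has the following drawbacks, shown for n = 20, SD 5, correlation 0.5 to 0.9 and an illustrative 2 mmHg margin (not a proposal):
- The investigators must commit to a margin.
- With true change 0 at every level, a mask returns no EPAP in 47–1% of trials, and at least one of four masks does so in 78–4%. At 3 mmHg these are 17–0% and 41–0%.
- In the same case all four levels pass, giving the correct answer of EPAP 0, in 22–96% of trials. The remainder, 100 − 22 − 47 = 31% down to 100 − 96 − 1 = 3%, return too high a level.
- Error is held per mask only. If EPAP 0 is truly at the margin and the other levels at 0, EPAP 0 is wrongly returned in 4–5% of trials for one mask and in 10–15% for at least one of four.
- One early baseline serves a session of at least 4 × 15 + 3 × 5 = 75 minutes. A +1 mmHg drift cuts a single-setting pass from 53–99% to 22–61%. A −1 mmHg drift passes a setting truly at the margin in 22–61% of trials instead of 5%. A reading before each mask would limit this, if the periodic readings include the washout intervals.
- If rebreathing adds 3 mmHg and support removes 3, the setting still passes in 53–99% of trials.

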4.2. Sample Size

20 healthy subjects.

4.3. Inclusion criteria:

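### Comfort is rated after each EPAP setting but tested by mask alone with independent-group tests; the plan gives no rule for combining ratings and cannot detect mask differences that vary with EPAP

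*Combined protocol and SAP*

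**What the plan says.** Section 3 (Methods) tests four masks in every volunteer and sets the pressures: "EPAP levels will be 0, 2, 4, & 5 while IPAP remains at 5 higher than EPAP". Comfort is scored from 1 to 5, "5 being the most comfortable after 5 each EPAP setting". The timing words are garbled, but the rating is tied to each setting, so every mask yields several ratings per volunteer.

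Section 10 (Variables) names CO₂ clearance and comfort as dependent variables, then gives "Independent: NIPPV interface, level of EPAP".

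Section 12 (Analysis) summarises comfort by medians and interquartile ranges without naming a grouping. The only test is by mask: "Relationship between dependent variable comfort level and independent variable NIPPV interfaces will be analyzed a Kruskal-Wallis test". If that is significant, a "Mann-Whitney U Test will be used to determine which masks were significantly more comfortable". Section 12 says nothing about comfort by EPAP, about how the ratings from one mask are combined, or about the pairing of ratings within a volunteer.

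**The concern.** Three things are missing from the comfort analysis.

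- **A combining rule.** With several ratings per volunteer and mask, the analyst could enter all of them, average them, or pick one setting. The plan leaves this open until the data have been seen.
- **The within-volunteer structure.** Kruskal-Wallis and Mann-Whitney assume independent groups. Here every volunteer rates every mask, and rates it more than once.
- **EPAP.** It is measured alongside comfort but used in no comfort test. Inspiratory pressure stays 5 above EPAP, so it runs from 5 to 10 cm H₂O across the settings. The Introduction links leak and over-tightening to discomfort, and reports different complaints by mask type. It is therefore plausible, though not established, that comfort changes with pressure more on some masks than on others.

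At stake is the statement of which masks are more comfortable. A single overall ranking could be read as holding at every pressure tested when it does not.

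**Working it through.** **Number of ratings.** Inputs: 20 volunteers (section 4.2), 4 masks and 4 EPAP levels (section 3).

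- Four settings per mask: 20 × 4 × 4 = 320 ratings, or 80 per mask, of which 40 are at EPAP 0 or 2.
- Section 3 allots 15 minutes per mask and samples EtCO₂ up to the 5:00 mark. If that means 5 minutes per setting, four settings need 4 × 5 = 20 minutes, and 15 / 5 = 3 settings fit. Three settings give 20 × 4 × 3 = 240 ratings.

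The count of 320 is therefore conditional. The point holds for any number of settings above one.

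**What an overall comparison can hide (hypothetical).** Let comfort on mask X be 5 − s × EPAP, and let mask Y be constant at X's mean. The mean EPAP is (0 + 2 + 4 + 5) / 4 = 2.75, so X minus Y at a given EPAP is s × (2.75 − EPAP), and the overall difference is 0.0 by construction. With s = 0.4, X scores 5.0, 4.2, 3.4 and 3.0, with mean 15.6 / 4 = 3.9. The documents give no slope, so a range is shown:

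| Slope s per cm H₂O | EPAP 0 | EPAP 2 | EPAP 4 | EPAP 5 | Overall |
|---|---|---|---|---|---|
| 0.1 | +0.275 | +0.075 | -0.125 | -0.225 | 0.0 |
| 0.2 | +0.55 | +0.15 | -0.25 | -0.45 | 0.0 |
| 0.4 | +1.1 | +0.3 | -0.5 | -0.9 | 0.0 |

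**Effect on the observed ranking (simulation).** There were 4,000 simulated trials per scenario, with 20 volunteers, 4 masks, 4 EPAP levels and ratings rounded to 1–5. Assumed, not from the documents: volunteer SD 0.7, volunteer-by-mask SD 0.5, residual SD 0.5. The figures give how often one mask's mean rating exceeds a comparator's. They describe the observed order, not significance.

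| Assumed true difference | Overall difference | Ahead, all EPAP levels | Ahead, EPAP 4 and 5 only |
|---|---|---|---|
| +0.5 at EPAP 0, 2; -0.25 at 4, 5 | (2 × 0.5 − 2 × 0.25) / 4 = 0.125 | 74% | 10% |
| +0.8 at EPAP 0, 2; -0.4 at 4, 5 | (2 × 0.8 − 2 × 0.4) / 4 = 0.2 | 85% | 2% |
| +1.0 at EPAP 0, 2; -0.5 at 4, 5 | (2 × 1.0 − 2 × 0.5) / 4 = 0.25 | 90% | 0.4% |
| +0.4 at every EPAP (additive) | 0.4 | 98% | 97% |

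The order reverses only when the mask difference itself changes sign with EPAP.

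**The planned test under no mask difference.** Rejection rates at an assumed two-sided 0.05 (the plan states no alpha), varying the volunteer-by-mask SD:

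| Volunteer-by-mask SD | Kruskal-Wallis, all 80 ratings per mask | Kruskal-Wallis, volunteer means | Friedman, volunteer means |
|---|---|---|---|
| 0 | 0.1% | 0.0% | 5.2% |
| 0.3 | 2.0% | 0.0% | 4.4% |
| 0.5 | 12.0% | 0.2% | 5.2% |
| 0.8 | 28.2% | 0.6% | 4.8% |

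The two ways of running Kruskal-Wallis give very different error rates, and neither holds 5% across the range. On volunteer means it is also weak: with the additive 0.4-point advantage above it rejects in 9% of trials, against 45% for Friedman on the same means.

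**The case against.** The strongest reply is that the stated aim is comfort with each mask, and a by-mask comparison answers that. No section says comfort is to be judged at the EPAP that clears CO₂. Section 10 lists the variables without promising to test every pairing. This stands: the overall mask comparison is a legitimate main analysis.

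The second reply is that every mask is meant to be tested at the same EPAP levels, so pressure does not bias the comparison. This also stands, and the additive scenario confirms it. A reader might infer that the by-mask test is confounded by EPAP; the documents do not support that.

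Third, the numerical examples are constructed. Nothing in the documents supports a loss of 0.4 points per cm H₂O on one mask and none on another. That is accepted: they show what is possible, not what is expected.

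Fourth, a reader might infer that the plan averages comfort over pressures it will find inadequate. The text names no averaging. It also sets no EtCO₂ criterion for adequate washout and tests EtCO₂ by EPAP without mask, so no inadequate level for a given mask could be identified as the analysis is written.

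Finally, the medians might be broken down by EPAP, and the procedure figure, which is not visible in the text available, might settle the timing. Neither would supply a test involving EPAP, a combining rule or a paired analysis. Those omissions remain.

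**Conclusion.** The concern holds as an omission and a mismatch of method, not as a wrong question. Comfort is measured at several EPAP settings in the same people, yet the plan tests it by mask alone, with tests for independent groups and no stated way to combine ratings.

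The consequence for the ranking is conditional. If mask differences in comfort vary with EPAP, the overall order can differ from the order at the higher settings, and the plan could not detect it. The size is hypothetical: an overall difference of 0.0 can conceal +1.1 to -0.9 points at a slope of 0.4, or +0.275 to -0.225 at a slope of 0.1. Without such an interaction the ranking is essentially unchanged (98% against 97%).

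The consequence for the test does not need an interaction. Under the assumed SDs, the null rejection rate runs from 0.0% to 28.2% depending on how the ratings are entered and how strongly they cluster within volunteer and mask.

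A reader might go further and conclude that the planned mask ranking is invalid, or that comfort must be compared at the EPAP that clears CO₂. The documents support neither.

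**What to change.** In section 12, replace Kruskal-Wallis and Mann-Whitney for comfort with a within-volunteer analysis, and state how the ratings are combined. Either of these would serve:

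- an ordinal mixed model with mask, EPAP and mask-by-EPAP, and volunteer effects (preferably including volunteer-by-mask), with the overall mask effect defined as the equally weighted average over the EPAP settings; or
- a Friedman test on each volunteer's mean rating per mask, with paired follow-up tests adjusted for the 6 mask pairs.

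Keep the overall by-mask comparison as the main one. Report the median and interquartile range of comfort for each mask at each EPAP. Show how mask differences change with EPAP, with intervals, as exploratory. Testing all pairs at each of four settings would be 6 × 4 = 24 comparisons, which 20 volunteers cannot support as confirmatory.

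Compare masks at an EPAP that clears CO₂ only if an EtCO₂ clearance criterion is fixed in advance; that would be a separate addition to the plan.

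In section 3, reconcile the 15 minutes per mask, the 5:00 sampling mark and the four EPAP levels, and clarify the comfort timing phrase, so that the number of ratings per mask is known.

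The cost is analysis wording only, with no ratings beyond those already planned. The downside is that the interaction will be imprecise with 20 volunteers, which is why it should be shown with intervals.
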